1.0 Project Summary/Abstract

Our long-term goal is to demonstrate the effectiveness of acupuncture for the treatment of adults with chronic pain of sickle cell disease (SCD), a debilitating pain syndrome characterized by acute and chronic pain. The objective of this study is to explore the feasibility and acceptability of acupuncture with adult sickle cell patients. We will conduct the study with adults with chronic pain from SCD, 18 years old or greater. They will all receive acupuncture. Treatments will be twice weekly for 5 weeks for 30 minutes. At baseline and post-treatment, subjects will complete measures that include pain, fatigue, anxiety, depressive symptoms, injustice experience, pain catastrophizing, and be interviewed about their feelings about receiving acupuncture. Subjects will also complete a measure of study acceptability, the Protocol Acceptability Scale for Treating SCD with Acupuncture at post-treatment. We will describe the procedures and potential challenges to implementing the acupuncture protocol and the range in the subjects' Acceptability Scale scores. We expect to identify and rectify any procedural problems subjects will report regarding the 10-session study protocol.

2.0 Background/Scientific Rationale

Every 30 minutes, every day, a person dies from a prescription opioid overdose in the United States (US). Further, opioid use is associated with a myriad of adverse outcomes.¹ Sickle cell disease (SCD) affects millions of people worldwide and is the most common lethal genetic blood disorder in the US, affecting about 100,000 people, mostly people of African and Hispanic background. Pain is the most common complication of SCD and is also a marker of clinical severity.² People with SCD are a population living with a high burden of chronic pain, high prescription opioid use,³ and health care disparities.⁴ Many with SCD are treated long term with oral opioids and when hospitalized for acute pain are treated with parenteral opioids.

Given this level of opioid use, it is crucial to consider complementary and integrative health (CIH) therapies as a method to decrease exposure to opioids while maintaining adequate pain control. One CIH therapy shown to be acceptable to people with SCD is acupuncture. Acupuncture typically involves inserting small needles into specific points on the body.¹ It is shown to decrease pain and provide an alternative to opioid use.²⁻⁴ Importantly, it is now covered by Medicare and Medicaid and is thus widely available and no longer tied to socioeconomic disadvantage. If successful, our project will drastically improve clinic-based pain management and help to reduce reliance on opioids and prevent opioid use disorder.

Acupuncture

There are few studies of acupuncture for the treatment of SCD. Two were pediatric studies^{5,6} and both reported pain reduction. A third study, which was an uncontrolled retrospective review, treated a total of 24 inpatient and outpatient adults during acute vaso-occlusive crisis with individualized acupuncture point prescriptions.⁷ Nine inpatients received a median of 3 treatments and had a reduction in pain of 2.1 on a 0-10 pain rating scale. Fifteen outpatients received a median of 4 treatments and had up to a 75% reduction in pain. The fourth uncontrolled study treated 10 adults with a total of 16 acute vaso-occlusive crises; subjects reported a decrease in pain in 15 of 16 acute vaso-occlusive crises.⁸ Because there have been only two trials on using acupuncture for adults with SCD, it is important to generate data on feasibility, acceptability, and protocol revisions for a future fully powered RCT of a standardized acupuncture protocol.

3.0 Objectives/Aims

Aim: To determine the feasibility (recruitment, retention, completion) and acceptability of performing acupuncture on 15 adult subjects with SCD.

Hypothesis: Acupuncture therapy will be feasible (80% recruitment, retention, completion) and acceptable to adults with SCD.

Impact: Acupuncture therapy has the potential to significantly reduce the pain and associated symptoms of SCD by offering therapy that is complimentary to optimal medical management. Symptom management is critical for reducing disability and improving quality of life for people with SCD.

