5.0 Subject Enrollment

- The primary providers at the UI Health SCD clinic will determine if a patient is eligible for the study.
- Eligibility will be assessed using the Eligibility Checklist. (See Appendix A for Eligibility Checklist).
- The PI or other key research personnel will give out a flyer describing the study to each eligible patient during clinic visits, and explain the general aspects of the study. The flyer also has a contact number for potential subjects to use if interested.
- Patients who express an interest in the study will meet with the PI or other key research personnel, who will explain the study in detail, answer questions, and obtain informed consent.
- Upon consent, patients will be administered baseline study measures.

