6.0 Study Design and Procedures

- This study is an unblinded, uncontrolled feasibility study.
- All subjects will receive acupuncture.
- Baseline measures will be taken prior to insertion of the acupuncture needles.
- The research assistant will confirm the subject's assigned code number before the start of each acupuncture session.
- The subject will lay face up on the acupuncture exam table.
- The acupuncturist will swab each of 18 acupuncture points with alcohol.
- Needle insertion will then be performed with a tapping in technique. The needles will be retained for 30 minutes; they will be twirled 3 times throughout the treatment. The needles will then be pulled.
- After the 10th acupuncture treatment the subject will complete data collection tools.

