9.0 Data Analysis

- Descriptive statistics will be conducted. Descriptive statistics (frequency, percentage, means, and standard deviations) were summarized at baseline. We reported pain intensity, pain interference and other pain related outcomes before and after the acupuncture intervention.

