12.0 Statistical Considerations

- This is a feasibility study and has not been powered. The data will be descriptive in nature.

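### The 80% feasibility hypothesis has no measure of precision: at 15 subjects an observed 12/15 has an exact 95% CI of 52% to 96%, so reaching 80% does not by itself demonstrate feasibility.

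*Combined protocol and SAP*

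**What the plan says.** The single aim in section 3.0 is "To determine the feasibility (recruitment, retention, completion) and acceptability of performing acupuncture on 15 adult subjects with SCD". Attached to it is this statement: "Hypothesis: Acupuncture therapy will be feasible (80% recruitment, retention, completion) and acceptable to adults with SCD". It gives no denominators, does not say whether 80% is a minimum, and names no confidence level.

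Section 2.0 explains what the results are for: "it is important to generate data on feasibility, acceptability, and protocol revisions for a future fully powered RCT of a standardized acupuncture protocol".

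Section 9.0 plans descriptive statistics: "Descriptive statistics (frequency, percentage, means, and standard deviations) were summarized at baseline". It adds pain intensity, pain interference and related outcomes before and after treatment, but does not name recruitment, retention or completion. Section 12.0 reads: "This is a feasibility study and has not been powered. The data will be descriptive in nature".

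On recruitment, section 5.0 says that study staff "will give out a flyer describing the study to each eligible patient during clinic visits". It does not say how many such patients there will be, or that they form the denominator of the recruitment rate.

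**The concern.** The study's only numeric hypothesis has no planned statement of how precisely 15 people can answer it. The proportion summaries that 9.0 lists are frequencies and percentages. Under that plan, 12 of 15 subjects retained could be reported as 80%, in line with the hypothesis, and nothing beside it would show how wide a range of true rates fits that result.

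The consequence falls on the later trial. Retention and completion rates from this study are natural inputs to its sample size and budget. If 80% is carried forward as established when the true rate is well below it, the allowance for drop-out in the RCT will be too small.

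**Working it through.** The plan states no power, precision or sample-size derivation, so it has no figure to reproduce. The check asks what an observed 80% means at this sample size.

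**Inputs**
- N = 15 enrolled subjects (3.0).
- Benchmark 80% (3.0).
- Assumption: retention and completion are proportions of the 15 enrolled. The plan does not say so.
- Assumption: meeting 80% means an observed proportion of at least 80%. Since 0.80 × 15 = 12, that is 12 or more of 15.
- Assumption: 95% confidence. The plan sets no level, so two-sided and one-sided results are both shown.

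**Step 1. Exact (Clopper-Pearson) limits.** For x of 15, the two-sided 95% lower limit is the p that solves P(X ≥ x | 15, p) = 0.025. The upper limit solves P(X ≤ x | 15, p) = 0.025. The one-sided 95% lower bound uses 0.05 in place of 0.025. For x = 15 the lower limits have a closed form: 0.025^(1/15) = 0.782 and 0.05^(1/15) = 0.819.

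| Observed | Rate | Two-sided 95% CI | One-sided 95% lower bound |
|---|---|---|---|
| 12/15 | 80.0% | 51.9% to 95.7% | 56.0% |
| 13/15 | 86.7% | 59.5% to 98.3% | 63.7% |
| 14/15 | 93.3% | 68.1% to 99.8% | 72.1% |
| 15/15 | 100% | 78.2% to 100% | 81.9% |

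For retention at 12/15, the observed loss is 20% and the interval for the loss runs from 100 − 95.7 = 4.3% to 100 − 51.9 = 48.1%.

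**Step 2. How often a lower true rate reaches 12/15.** P(X ≥ 12 | 15, p) is the sum over k = 12 to 15 of C(15,k) p^k (1−p)^(15−k). At p = 0.70 the four terms are:
- k = 12: 455 × 0.7^12 × 0.3^3 = 0.170
- k = 13: 105 × 0.7^13 × 0.3^2 = 0.092
- k = 14: 15 × 0.7^14 × 0.3 = 0.031
- k = 15: 0.7^15 = 0.005

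The unrounded terms sum to 0.297. The same sum gives 0.46 at p = 0.75 and 0.09 at p = 0.60.

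**Step 3. Recruitment.** Its denominator could be all eligible patients given the flyer, those approached in detail, or the enrolment target of 15. The plan does not say which, so no interval can be computed for it now.

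**The case against.** The strongest defence is that the study claims little. Section 6.0 says "This study is an unblinded, uncontrolled feasibility study", section 12.0 declares it unpowered and descriptive, and section 1.0 speaks of exploring feasibility and correcting procedural problems. A reader given n/N can also work out an interval unaided. This stands as a limit on severity: there is no failed test, and 15 subjects need no power justification here. It does not remove the point, because an interval is itself a descriptive summary and asks for no power and no more patients. Section 3.0 also goes beyond description by stating a hypothesis with a number in it.

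A reader might infer four stronger things that the documents do not support.

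- **That the study applies a go/no-go rule with a high error rate.** No such rule is stated, and 12 of 15 is only a reading of 80%. One could compute that a protocol with a true rate of exactly 80% falls short of 12/15 about 35% of the time (1 − 0.648 = 0.352). That comes from placing the truth at the cut-off: the corresponding figure is 37% at N = 20 and 42% at N = 50. It is not evidence that 15 is too few, and an interval would not change it.
- **That the figures hold for all three criteria.** They cannot be attached to recruitment, for the reason in step 3. A joint probability of meeting several criteria is not supportable either, since the plan does not say how they relate and completers may be nested within those retained.
- **That even a perfect 15/15 could not exclude a rate below 80%.** This depends on the method. The two-sided 95% exact limit (78.2%) is below 80%, but the one-sided 95% exact bound (81.9%), a natural choice for a minimum, is above it. The plan specifies neither.
- **That the plan commits to judging feasibility on bare percentages.** Section 9.0 ties its listed statistics to baseline and does not mention the three rates. The plan is silent on how they will be analysed.

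**Conclusion.** The point holds for retention and completion, on the assumption that both are taken out of 15. An observed 80% is then compatible, at two-sided 95% exact confidence, with true rates from 52% to 96%, and a true rate of 70% reaches 12/15 about 30% of the time. Reporting that 80% was reached does not by itself demonstrate feasibility, and the plan provides nothing that would show the reader this. For recruitment, what can be said is that the denominator and the precision are both unstated.

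The interval should not be overstated in the other direction: at a true rate of 50%, 12 or more of 15 has probability 0.018, so the two-sided 95% interval just excludes 50%.

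This is a worthwhile correction to reporting and wording. The study can run as designed, but without the change its main conclusion is open to over-reading.

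**What to change.** In section 9.0, add that recruitment, retention and completion will each be reported as n/N with an exact (Clopper-Pearson) two-sided 95% confidence interval. State the denominators: enrolled subjects for retention and completion, and eligible patients approached for recruitment. The number approached has to be logged for the last of these.

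In section 3.0, word 80% as a planning benchmark against which each rate will be estimated. Say that planning of the future RCT will consider the interval and not only whether the point estimate reaches 80%. This also brings 3.0 into line with the descriptive intent of 12.0.

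The cost is a few sentences of protocol text and a few lines of analysis, plus a count of patients approached if none is kept already. No extra subjects or visits are needed. The drawback is a less favourable headline: 12/15 would be reported as 80% (52% to 96%) and would no longer read as feasibility shown.

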4.0 Eligibility

- Adults with SCD who have had a moderate to severe level of pain (≥ 3 on 0-10 scale) related to SCD within the last 3 months, receiving care at the UI Health SCD clinic will be eligible to participate.

4.1 Inclusion Criteria

- Adults with SCD who have had a moderate to severe level of pain (≥ 3 on 0-10 scale) related to SCD within the last 3 months, receiving care at the UI Health SCD clinic will be eligible to participate.

4.2 Exclusion Criteria

- Pregnancy
- Physically or cognitively unable to complete the study procedures

5.0 Subject Enrollment

- The primary providers at the UI Health SCD clinic will determine if a patient is eligible for the study.
- Eligibility will be assessed using the Eligibility Checklist. (See Appendix A for Eligibility Checklist).
- The PI or other key research personnel will give out a flyer describing the study to each eligible patient during clinic visits, and explain the general aspects of the study. The flyer also has a contact number for potential subjects to use if interested.
- Patients who express an interest in the study will meet with the PI or other key research personnel, who will explain the study in detail, answer questions, and obtain informed consent.
- Upon consent, patients will be administered baseline study measures.

6.0 Study Design and Procedures

- This study is an unblinded, uncontrolled feasibility study.
- All subjects will receive acupuncture.
- Baseline measures will be taken prior to insertion of the acupuncture needles.
- The research assistant will confirm the subject's assigned code number before the start of each acupuncture session.
- The subject will lay face up on the acupuncture exam table.
- The acupuncturist will swab each of 18 acupuncture points with alcohol.
- Needle insertion will then be performed with a tapping in technique. The needles will be retained for 30 minutes; they will be twirled 3 times throughout the treatment. The needles will then be pulled.
- After the 10th acupuncture treatment the subject will complete data collection tools.

7.0 Expected Risks/Benefits

- Expected Risks: There is a risk of bruising or bleeding after the acupuncture needle is withdrawn. There is a risk that they may experience a negative reaction from acupuncture and thereby experience worse symptoms from participation in the study. If potential subjects are afraid of needles, they may not want to participate although the needles are very small. There is risk that some of the questions in the questionnaires may make the subject uncomfortable, nervous or tired. There is also the risk of loss of privacy or confidentiality, but we will avoid this and all other risks as much as possible.
- Expected Benefits: There may be no benefit to individual subjects, but the knowledge gained from this study is expected to help providers better manage SCD pain by having a better understanding of whether or not acupuncture reduces the pain of SCD.

9.0 Data Analysis

- Descriptive statistics will be conducted. Descriptive statistics (frequency, percentage, means, and standard deviations) were summarized at baseline. We reported pain intensity, pain interference and other pain related outcomes before and after the acupuncture intervention.

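### The 80% feasibility criterion lacks a secured recruitment denominator, and the schedule in 6.0, taken literally, hears acceptability only from subjects who finish all 10 sessions

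*Combined protocol and SAP*

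**What the plan says.** All references are to the combined protocol and SAP.

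- **Criterion (3.0).** The hypothesis is "Acupuncture therapy will be feasible (80% recruitment, retention, completion) and acceptable to adults with SCD". The aim refers to "acceptability of performing acupuncture on 15 adult subjects with SCD". None of the three rates is defined, and 15 is not stated to be the denominator of any of them.
- **Analysis (9.0, 12.0).** Section 9.0 opens with "Descriptive statistics will be conducted. Descriptive statistics (frequency, percentage, means, and standard deviations) were summarized at baseline" and continues "We reported pain intensity, pain interference and other pain related outcomes before and after the acupuncture intervention". It does not mention the three rates. Section 12.0 says the study is unpowered and descriptive. Section 1.0 plans to describe procedures, challenges and the range of acceptability scores.
- **Enrolment (5.0).** "Eligibility will be assessed using the Eligibility Checklist". Staff "will give out a flyer describing the study to each eligible patient during clinic visits", and then "Patients who express an interest in the study will meet with the PI or other key research personnel". No log of those approached, and no record of those who decline or never respond, is required. The checklist in Appendix A has no field for enrolment outcome. Storage is specified for questionnaires (11.0) and consent documents (13.1), but not for the checklists of patients who do not enrol.
- **Post-treatment data (6.0, 8.0).** Section 6.0 states "After the 10th acupuncture treatment the subject will complete data collection tools". The table in 8.0 instead places the acceptability scale after the subject's final session, without naming the 10th. Section 1.0 says post-treatment. No section describes what is collected from a subject who stops early.

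**The concern.** Feasibility and acceptability are the study's whole aim, so the data behind them matter more here than the pain summaries do.

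Recruitment can be read in at least three ways: consented over eligible patients given a flyer, consented over patients who express interest, or enrolled over the target of 15. Only the first shows how readily this clinic population takes up the study, and it is the one whose denominator the plan does not secure. A patient who takes a flyer and never calls leaves no required record.

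Acceptability has a similar gap. The scale in Appendix B asks whether taking part was too hard and whether the study was too long. Section 1.0 expects to find and correct procedural problems with the 10-session protocol, and 2.0 wants the results to shape changes before a later randomised trial. Subjects who stop early have direct experience bearing on those questions, and following 6.0 as written would leave them out.

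Retention is also undefined. Depending on its meaning, it either nearly duplicates completion or can differ from it enough to fall on the other side of 80%.

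**Working it through.** **Inputs.** From the documents: threshold 80% and target 15 (3.0); 10 sessions per subject (1.0, 13.1). The documents give no counts of patients approached, interested, withdrawn or stopping early. The values used for these below are assumptions, and consented is taken as equal to enrolled. The plan contains no calculation of the three rates to reproduce.

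**1. Recruitment among those approached.** Rate = enrolled / D, where D is the number of eligible patients given a flyer. The condition 15/D ≥ 0.80 gives D ≤ 15/0.80 = 18.75, so D is at most 18.

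| D (assumed) | 15/D |
|---|---|
| 15 | 100% |
| 18 | 83% |
| 19 | 79% |
| 20 | 75% |
| 25 | 60% |
| 30 | 50% |
| 40 | 38% |
| 60 | 25% |

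Enrolled over target is 15/15 = 100% whatever D is. If only 12 enrol, 12/15 of target = 80% meets the criterion, but the flyer-based rate does so only if D ≤ 12/0.80 = 15. The two readings agree only when few patients beyond those enrolled were approached.

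**2. Who answers the acceptability scale.** 80% of 15 is 0.80 × 15 = 12, so the completion criterion can be met with 15 − 12 = 3 non-completers, or 3/15 = 20% of those enrolled. For a subject who finishes, the timings in 6.0 and 8.0 coincide. For one who stops after, say, session 4, the final session has occurred but the 10th treatment has not: 8.0 could include that subject, while 6.0 followed literally would not. The planned range of scores would then describe finishers only.

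**3. Retention against completion.** Let 15 enrol, w withdraw, and m stay in the study but miss sessions.

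- Completion (all 10 sessions) = (15 − w − m)/15, which is at least 80% when w + m ≤ 3.
- Retention as not withdrawn = (15 − w)/15, which is at least 80% when w ≤ 3.

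The two verdicts differ whenever w ≤ 3 and w + m > 3. Illustration with w = 2 and m = 2: completion is 11/15 = 73% and retention is 13/15 = 87%.

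If retention means post-treatment data obtained, the same subjects give 11/15 = 73% when 6.0 is followed literally. They would give 15/15 = 100% if early stoppers were all asked and all answered, because the 2 who withdrew would then count as retained. Withdrawal status and data return therefore need separate lines.

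**The case against.** The strongest reply is that this is a small, unpowered, descriptive study. Counts of the three rates are surely intended, and the general promise of descriptive statistics covers them. Much of that stands. Lack of power is not a defect here, and a reader who infers from 9.0 that the rates will not be reported goes further than the text. The reply does not supply a count of patients approached if none is kept.

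Several stronger readings are tempting and should be resisted:

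- **That completion is ambiguous.** It has an obvious reading, all 10 sessions over enrolled. Session counts are probably recoverable, because codes are confirmed at each session (6.0) and forms are reviewed on an ongoing basis (10.0).
- **That 6.0 bars early stoppers from being asked.** It does not. It describes the full course and is silent about anyone who leaves it, and the wording in 8.0 is open to including them.
- **That acceptability will be inflated by a known amount.** The ten-item scale has no scoring cut-off, so a percentage favourable, or bounds on one, cannot be calculated from the plan. Even the direction is plausible rather than shown: a subject may stop for reasons unrelated to acceptability.
- **That definitions will be chosen after seeing results.** The past tense in 9.0 may prompt this inference, but the documents do not establish when definitions were or will be fixed.

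**Conclusion.** The concern holds as a gap in data collection and reporting, and it should be fixed. A recruitment rate among eligible patients approached may not be computable from what 5.0 requires. With 15 enrolled, the verdict on 80% turns on whether more than 18 were approached, while enrolled over target would be 100% regardless. Acceptability of the 10-session protocol may be heard from finishers only if 6.0 is followed literally, with a risk, not a demonstrated bias, of looking too favourable. Retention needs one stated meaning, because plausible meanings can fall on opposite sides of 80%.

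The threshold of 18 rests on 15 being enrolled. The other approach counts and the withdrawal pattern are illustrations. The conclusion about early stoppers depends on 6.0 being applied as written and on some subjects stopping early.

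**What to change.** 1. **Section 5.0.** Keep every Eligibility Checklist and tally each eligible patient given a flyer with the outcome (no response, declined, consented). Report recruitment as consented over eligible patients given a flyer. If enrolment is finished, reconstruct the count from stored checklists, or state that it is unavailable and report enrolled over target under that label.
2. **Sections 6.0 and 8.0.** Reconcile the two timings so that the acceptability scale and post-treatment questionnaires are also sought from enrolled subjects who stop early. Report the planned range of scores separately for finishers and early stoppers, with the number of enrolled subjects not answering. If data collection is finished, report that number.
3. **Section 9.0.** Report the aim's rates as n/N. Over enrolled, completion is all 10 sessions received and retention is not withdrawn from the study. Show the proportion giving post-treatment measures on its own line, so that a withdrawn subject who returns a questionnaire is not counted as retained. If these definitions are fixed after data have been seen, say so. An exact 95% interval is optional (for example, 12/15 = 80%, interval 52% to 96%).

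**Cost.** If the study is open: a one-page tally sheet, one contact per early stopper with some burden and some non-response, and short edits to four sections. If it is finished: a count from stored forms and a statement of what is missing. Recruitment and acceptability may look less favourable as a result.
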